9.1 Statistical methods

All patients will have their salivary output measured before radiotherapy, 3 weeks after the start of radiotherapy, and at the end of radiotherapy (6 weeks). Patients with clinically severe gland dysfunction (i.e., those with loss of at least 50% of the pre-radiotherapy value) will be eligible for everolimus treatment. Follow-up measurements will be obtained prior to everolimus administration, at completion of the 5 day everolimus course at 1 month, 3 months and 6 months after RT/chemoRT completion.

The primary end point of the analysis will be the percent recovery of salivary gland function, with pre-everolimus treatment saliva flow rate as the denominator and the saliva flow rate at 3 months after completion of radiation or chemoradiation therapy as the numerator.

It is our expectation that because of the short exposure to everolimus (a total of 5 days only), the well described everolimus related toxicities will not develop.

However, following discussions with the company (Novartis), two dose levels will be evaluated: a starting dose of 5 mg po daily, will initially be evaluated in a cohort of 3 patients.

For the purpose of this trial, dose-limiting toxicity (DLT) is defined as an everolimus-related grade 3 or higher AE.

Toxicity will be graded based on the Common Terminology Criteria for Adverse Events (CTCAE) Version 4.03.

(<http://www.hrc.govt.nz/sites/default/files/CTCAE%20manual%20-%20DMCC.pdf>)

As mentioned, we will start treating enrolled patients on the lower dose level.

-If no DLT occurs, will proceed with dose escalation to the full FDA-approved dose (10 mg po daily) [in this case, total number of patients in the trial: 13; 3 in the 5 mg cohort, 10 in the 10 mg cohort].

-If 1 DLT occurs, cohort will be expanded to additional 3 patients; and if another DLT occurs in this expanded cohort, no escalation to full dose (10 mg po daily) will be attempted, and cohort will be expanded to 10 patients [in this case, total number of patients in the trial: 10; all in the 5 mg cohort];

and if no additional DLT occurs in the expanded cohort, dose escalation to full dose (10 mg po daily) will follow [in this case, total number of patients in the trial: 16; 6 in the 5 mg cohort, in the 10 mg cohort].

-If 2 DLT occur, no escalation to full dose (10 mg po daily) will be attempted, and cohort will be expanded to 10 patients.) [in this case, total number of patients in the trial: 10; all in the 5 mg cohort].

As a result of these possibilities, total number of patients included in this phase 0, proof of principle trial can range from a minimum of 10 to a maximum of 16 total patients.

Maximum number of 16 patients will occur if a DLT occurs in one of the first 3 patients in the 5 mg cohort, and no DLT occurs in the additional 3 expanded cohort patients (for a total of 6 patients in the 5 mg cohort). Subsequently, 10 additional patients will be enrolled in the 10 mg cohort, for a maximum total of 16 patients.

Planned analyses will be performed by strata (patients enrolled at the 5 mg dose level versus the 10 mg dose level).

Statistical analysis will compute the mean percent recovery of all treated patients (with a 95% confidence interval). Ten patients at the selected dose will allow estimating the mean percent recovery with standard error that is 0.32 of the observed standard deviation. Exploratory analysis will determine if any clinical factors are predictive of treatment response, specifically ipsilateral vs bilateral neck irradiation. Changes in the secondary endpoints across time, including the saliva flow rates, saliva protein composition, total score obtained on the Xerostomia Inventory survey, and total score on the Xerostomia Visual Analog Scale survey, will be explored using graphical methods.

10 Protocol amendments, or changes in study conduct

Any change or addition (excluding administrative) to this protocol requires a written protocol amendment that must be reviewed by Novartis and the investigator before implementation. Amendments significantly affecting the safety of subjects, the scope of the investigation or the scientific quality of the study require additional approval by the IRB at each study center. A copy of the written approval of the IRB must be provided to Novartis. Examples of amendments requiring such approval are:

1. increases in drug dose or duration of exposure of subjects,
2. significant changes in the study design (e.g. addition or deletion of a control group),
3. increases in the number of invasive procedures,
4. addition or deletions of a test procedure required for monitoring of safety.

These requirements for approval should in no way prevent any immediate action from being taken by the investigator or by Novartis in the interests of preserving the safety of all patients included in the trial. If an immediate change to the protocol is felt to be necessary by the investigator and is implemented for safety reasons Novartis must be notified and the IRB at the center must be informed immediately. Amendments affecting only administrative aspects of the study do not require formal protocol amendments or IRB approval but the IRB must be kept informed of such administrative changes. Examples of administrative changes not requiring formal protocol amendments and IRB approval include:

1. changes in the staff used to monitor trials
2. minor changes in the packaging or labeling of study drug.

11. Data and Safety Monitoring Plan

11.1 Identification of the DSMB obligated for oversight responsibilities:

The University of Arizona Cancer Center Data and Safety Monitoring Board (DSMB) will provide ongoing oversight for this trial. This study has been assigned a High Risk level by the DSMB.

11.2 Identification of the entity obligated for routine monitoring duties:

Routine monitoring will be provided by The University of Arizona Cancer Center Quality Assurance/Quality Control (QA/QC) Program to ensure that the investigation is conducted according to protocol design and regulatory requirements.

Data from each subject visit will be entered into the OnCore system within 1 week of the subject visit.

This trial will also undergo real-time monitoring by the PI and study team, including documentation of real-time monitoring of any new or ongoing safety issues. Weekly conference calls will be conducted with PI and study staff to address the following:

- adverse events (including serious adverse events):

IRB NUMBER: PHXB-17-0072-70-15
IRB APPROVAL DATE: 07/03/2018

- screening and enrollment including cohort management.
- protocol deviations and corrective action plans for any identified deviations
- accuracy and timeliness of data collection/entry

11.3 Monitoring progress and data review process:

Routine monitoring of subject data will be conducted at least every month.

The first routine monitoring visit will include at a minimum:

- Informed consent – 100% of cases enrolled;
- Subject eligibility – 100% of cases, up to three subjects;
- Data review – 100% of cases, up to three subjects.

All subsequent monitoring visits will consist of randomly selected subject cases based on current enrollment and include continuing review of previously selected cases, as applicable.

A monitoring visit report and follow-up letter will be completed approximately two weeks after the routine monitoring visit; a copy will be maintained in the study file. The monitor will request additional source documentation, clarification, information, or corrections to the CRF and/or regulatory records from the Clinical Research Coordinator (CRC) or other applicable staff responsible for the study and resolution of queries/findings. Documentation of such a request will be maintained with a copy of the monitor's visit report for follow-up at the next monitoring visit. Electronic records will be available in the institutional database or provided by the QA/QC Program staff.

The Principal Investigator will ensure the accuracy, completeness, legibility and timeliness of the data reported in the Case Report Form (CRF), or other acceptable data formats. Source documentation supporting the study data should indicate the subject's participation in the trial and should document the dates and details of study procedures, adverse events, and patient status.

All Case Report Forms (CRF) will be entered into the institutional database and completed electronically.

Note: Routine monitoring of regulatory documents will be conducted at least every six months, and routine monitoring of test article will be conducted at least every three months.

11.4 Process to implement study closure when significant risks or benefits are identified:

Please see section 9.1 for escalation and de-escalation procedure which may include study closure as determined by occurrence of dose limiting toxicities.

11.5 Plan for assuring data accuracy and protocol compliance:

Routine study activity and safety information will be reported to the DSMB on a monthly basis, or more frequently if requested. These reports will include:

- Study activity, cumulative and for the period under review;
- Safety (narrative description on non-serious and serious adverse events, protocol pre-determined early stopping rules for safety or treatment-emergent adverse events);
- Predetermined protocol early stopping rules for efficacy/futility;
- Status of study in relationship to stopping rules;
- Current dose level of study agent;

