Impact: Reduction in saliva production and oral dryness can have a devastating effect on oral health that potentially leads to malnutrition and poor quality of life. Common palliative therapies for xerostomia include oral lubricants, saliva substitutes, and saliva stimulants (gum, pilocarpine). Unfortunately, these therapies are short-lived and have not consistently demonstrated the ability to relieve xerostomia symptoms. Therefore these patients are left with very few options and this research could provide a long-term solution for these individuals.

This research project brings together a newly-formed, diverse, interdisciplinary team to solve this complex problem. This team takes advantage of the expertise at both Banner – University Medical Center and St. Joseph's Hospital and Medical Center and the ability to recruit patients in Phoenix and Tucson. It extends the mouse model work conducted by the [name] lab to a phase 0 “proof of principle” clinical trial.

Rapamycin derivatives exhibit considerable similarities in mechanism of action constituting a drug class effect. Therefore, this trial is proposing the use of everolimus due to the ease of administration (orally), which we postulate will have similar biological effects as CCI-779. If successful, the opportunity to expand to a randomized, placebo-controlled, double-blind clinical trial is envisioned.

3 Objectives and endpoints

Initial Objective

Document the safe everolimus dose (5 mg versus 10 mg) to be used in the post radiation or chemoradiation setting for salivary function restoration, using a 3 + 3 design.

Once the safe dose has been defined:

Primary Objective

To describe the recovery of salivary gland function after administration of a 5-day course of everolimus, administered two weeks after completion of radiation or chemoradiation therapy

Primary endpoint

The primary end point of the analysis will be the percent recovery of salivary gland function, with pre-everolimus treatment saliva flow rate as the denominator and the saliva flow rate at 3 months after completion of radiation or chemoradiation therapy as the numerator.

Secondary Objectives

- To describe the decrease of saliva flow rates during radiation or chemoradiation therapy
- To describe the changes in saliva protein composition during radiation or chemoradiation therapy and following administration of a 5-day course of everolimus

Secondary endpoints

Secondary endpoints will be:

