- the decrease of saliva flow rates (compared to baseline prior to definitive treatment) during radiotherapy treatment at 3, 6 weeks and prior to everolimus administration and the subsequent recovery of saliva flow rates at completion of the 5 day everolimus course and 1, 3 and 6 months after RT/chemoRT completion to determine the kinetics and stability of saliva flow rate recovery.
- protein composition within the saliva will be measured and will be expressed as percent decrease and recovery of amylase at all available time points.

- Xerostomia Visual Analog Scale survey and Xerostomia Inventory survey will be obtained from each participant at all available time points (See Appendix A and B).

4 Study design

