4.1 Description of study design

Patients treated with curative intent either in the post-operative or definitive setting with high dose radiotherapy (≥ 50 Gy) with or without chemotherapy will be eligible. There will be one treatment group with each patient serving as their own control. Patients would have their salivary output measured before radiotherapy, 3 weeks after the start of radiotherapy, and at the end of radiotherapy (6 weeks). Patients who demonstrate more than a 50% decrease in

saliva flow rates will enter the treatment phase of the trial. Based on expert experience, we estimate that half the treated patients will exhibit a decrease of 50% or more in flow rate. These affected patients will then receive the planned dose of everolimus **once a day for 5 days, starting two weeks after the completion of radiotherapy**. Salivary output measurements will be obtained prior to everolimus administration and at completion of the 5 day everolimus course and at 1 month, 3 months and 6 months after the completion of radiation or chemoradiation therapy.

It is our expectation that because of the short exposure to everolimus (a total of 5 days only), the well described everolimus related toxicities will not develop.

However, following discussions with the company (Novartis), two dose levels will be evaluated: a starting dose of 5 mg po daily, will initially be evaluated in a cohort of 3 patients.

For the purpose of this trial, dose-limiting toxicity (DLT) is defined as an everolimus-related grade 3 or higher AE.

Toxicity will be graded based on the Common Terminology Criteria for Adverse Events (CTCAE) Version4.03.

(<http://www.hrc.govt.nz/sites/default/files/CTCAE%20manual%20-%20DMCC.pdf>)

As mentioned, we will start treating enrolled patients on the lower dose level.

-If no DLT occurs, will proceed with dose escalation to the full FDA-approved dose (10 mg po daily) [in this case, total number of patients in the trial: 13; 3 in the 5 mg cohort, 10 in the 10 mg cohort].

-If 1 DLT occurs, cohort will be expanded to additional 3 patients; and if another DLT occurs in this expanded cohort, no escalation to full dose (10 mg po daily) will be attempted, and cohort will be expanded to 10 patients [in this case, total number of patients in the trial: 10; all in the 5 mg cohort];

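### The dose-level grouping in Section 9.1 has no exception, so as written it describes saliva loss during radiotherapy only in patients selected for losing at least 50%

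*Protocol*

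**What the plan says.** Section 3 gives as a secondary objective "To describe the decrease of saliva flow rates during radiation or chemoradiation therapy". The matching endpoint is "the decrease of saliva flow rates (compared to baseline prior to definitive treatment) during radiotherapy treatment at 3, 6 weeks and prior to everolimus administration", followed by the later recovery. Neither names a population.

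Section 9.1 says who is measured: "All patients will have their salivary output measured before radiotherapy, 3 weeks after the start of radiotherapy, and at the end of radiotherapy (6 weeks". It then says who may go on to the drug: "Patients with clinically severe gland dysfunction (i.e., those with loss of at least 50% of the pre-radiotherapy value) will be eligible for everolimus treatment". The Schema has the same two steps, with registration before radiotherapy and a second registration, with an eligibility check, before everolimus. Section 4.1 gives the expected yield: "we estimate that half the treated patients will exhibit a decrease of 50% or more in flow rate", where the context shows that the treated patients are those given radiotherapy.

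On analysis, Section 9.1 states that "Planned analyses will be performed by strata (patients enrolled at the 5 mg dose level versus the 10 mg dose level". No exception follows. The mean percent recovery is to be computed in all treated patients. The secondary endpoints, including flow, saliva protein and the two survey scores, are to be explored graphically, with no population given. The total of 10 to 16 patients counts only the 5 mg and 10 mg cohorts.

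**The concern.** A dose level exists only for a patient who passed the 50% threshold and went on to everolimus. A registered patient who kept more than half of the baseline flow has none, and no sentence gives that patient a place in any analysis. The only grouping rule in Section 9.1 therefore does not fit an objective about loss during radiotherapy, for two reasons.

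First, the threshold is set on the variable that the objective describes. A summary restricted to patients who passed it answers a narrower question than the objective asks, and gives a larger loss. Second, the dose is given about two weeks after radiotherapy ends. It cannot have affected readings taken before and during radiotherapy, so splitting them by dose carries no information and thins a small sample.

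At stake is the answer to one of two secondary objectives. So is the natural check on the protocol's estimate that half of patients lose 50% or more, a figure that would help in planning the randomized trial envisaged in Section 2.

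**Working it through.** **The plan's own precision figure.** Section 9.1 says that ten patients give a standard error of 0.32 of the standard deviation. SE/SD = 1/√10 = 0.316, which agrees. The figure concerns percent recovery after everolimus; none is given for loss during radiotherapy.

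**Inputs from the protocol.** Threshold: at least 50% loss (Section 9.1). Share expected to reach it: one half (Section 4.1). Patients dosed: 10 to 16 (Section 9.1).

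**Assumed inputs.** The SD of percent loss is not given; 10 to 30 points is used. Loss is taken as normal with mean 50%, so that half the patients reach the threshold, and capped at 100%. End of radiotherapy is taken as the selection visit.

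**Patients left without a group.** Number registered = number dosed / 0.5: 10/0.5 = 20, 13/0.5 = 26, 16/0.5 = 32. If everyone eligible is dosed, 10 to 16 of the 20 to 32 patients measured during radiotherapy have no dose level.

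**Mean loss at the selection visit.** For patients between 50% and 100% loss,

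mean = 50 + SD × [φ(0) − φ(b)] / [Φ(b) − 0.5], with b = 50/SD.

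At SD 20, b = 2.5, so the mean is 50 + 20 × (0.3989 − 0.0175)/(0.9938 − 0.5) = 65.4%.

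| Assumed SD (points) | All registered | Dose groups only | Gap (points) |
|---|---|---|---|
| 10 | 50.0% | 58.0% | 8.0 |
| 15 | 50.0% | 61.9% | 11.9 |
| 20 | 50.0% | 65.4% | 15.4 |
| 25 | 50.0% | 68.1% | 18.1 |
| 30 | 50.0% | 69.9% | 19.9 |

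**If the share is not one half.** At SD 20, without the cap, mean loss in all patients against those selected is:
- share 30%: 39.5% against 62.7%
- share 50%: 50.0% against 66.0%
- share 70%: 60.5% against 70.4%
- share 90%: 75.6% against 79.5%

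The direction does not change. The gap narrows as more patients qualify.

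**Week 3.** Here selection acts only through the correlation ρ with end-of-radiotherapy loss. With an assumed week-3 mean of 35% and SD 20 at both visits, the selected mean is about 35 + ρ × 20 × √(2/π) = 35 + 15.96ρ. That gives 39.8% at ρ = 0.3 and 49.4% at ρ = 0.9. The loss is inflated, but values below 50% are possible. The same reasoning applies to amylase, the two surveys, and whichever of stimulated and unstimulated flow is not used for selection.

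**The case against.** The strongest reply is that nothing in the protocol says that this particular objective is analysed by dose. The rule is a general sentence placed directly after the dose-cohort counts. The next sentence speaks of all treated patients, and the sentence on secondary endpoints names only a graphical method. The population for a descriptive secondary endpoint is often settled in the SAP. It is right that the application to this objective is inferred. But the general sentence is unqualified, and the graphical-methods sentence gives a method without replacing the population. The complaint is about a grouping that the protocol does state and that does not fit its objective, rather than about a detail left for later.

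A second reply is that treated patients are the right set for a curve of loss followed by recovery, which is how Section 3 words the endpoint. This stands. The display by dose is valid as the treated patients' own course, and misleads only if read as loss in everyone irradiated.

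Several stronger readings are tempting but not supported:

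- A reader might infer that the data on undosed patients are thrown away. No text says so; all patients are to be measured through the end of radiotherapy, so the overstatement is avoidable.
- A reader might infer that every radiotherapy-phase result is forced to at least 50% loss. The floor holds only for the flow measure used for selection, at the selection visit.
- A reader might expect a change of population to remove a rise in flow between selection and the first dose caused by regression to the mean. That is a separate consequence of the threshold and would remain in the treated patients' curves.
- A reader might extend the point to the comparison of ipsilateral with bilateral irradiation. Section 9.1 asks whether that factor predicts treatment response, which undosed patients cannot inform. Studying radiotherapy loss by neck field would be an optional extra.

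**Conclusion.** The point holds in a limited form. Section 9.1 fixes one grouping for all planned analyses, and that grouping does not suit the objective of describing loss during radiotherapy. Followed as written, it leaves out about half of the patients measured and raises the mean loss at the selection visit from 50% to about 58-70%.

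The 50% threshold and the one-half share come from the protocol. The SDs of 10 to 30 points, the normal shape and the week-3 figures are assumptions. The direction follows from selecting on the outcome and does not depend on them; the size does.

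Severity is minor. The endpoint is secondary, descriptive and explored graphically, and the protocol ties no decision to it.

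**What to change.** In Section 9.1, limit the dose-level sentence to post-everolimus endpoints, and add wording such as:

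*Radiotherapy-phase endpoints (Visits 1 to 3: saliva flow, amylase, Xerostomia Inventory and VAS) will be described in all Step 1 patients with a baseline value, not split by dose level. The number and proportion losing at least 50% of baseline flow will be reported with an exact 95% confidence interval. The pre-everolimus reading and the later course will be described in treated patients and labelled as a selected group.*

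The reported proportion tests the one-half estimate in Section 4.1, though loosely. With 20 to 32 patients and a true share of one half, its standard error is √(0.25/20) = 0.11 to √(0.25/32) = 0.09.

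The cost is a short change to Section 9.1, carried into any SAP. No new visits or measurements are needed, because Section 9.1 already has all patients measured through the end of radiotherapy ("All patients will have their salivary output measured before radiotherapy" and at the two later readings).

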- 9) If the patient is too dry, (dry mouth), it is possible to add the weight of the gum base to the pre-weight measure with the gum base in the cup of saliva.

Analysis of saliva: The collection tubes are weighed before and after saliva collection. The difference equates to the total mL collected which is divided by the number of minutes of collection. Saliva is stored at -80°C for further analysis on salivary protein composition at a later date (described in correlatives below).

The comorbidity of mucositis is an important consideration in this study due to the development of this condition following radiotherapy and as a side effect from chronic use of everolimus. Treatment with everolimus has been designed to begin two weeks after radiotherapy to allow radiation-induced mucositis to start improving. In a pre-clinical model,

concurrent rapamycin treatment with radiotherapy (6Gy/day X 5 days) prevents mucositis due in part to increased expression of mitochondrial superoxide dismutase (MnSOD) (Iglesias-Bartolome 2012). Given the short duration of treatment in this trial (5 days), a delay in the start of everolimus until two weeks after radiotherapy and evidence from this pre-clinical study, we postulate that mucositis will not be a major concern. Patients will be closely monitored for worsening mucositis response once treated with everolimus and if mucositis worsens in 2 out of the first 6 patients, then everolimus 50% dose reduction will be implemented.

5 Population

Patients with locally advanced squamous cell carcinoma of the head and neck, treated with curative intent either in the post-operative or definitive setting with high dose radiotherapy (≥ 50 Gy) with or without chemotherapy will be eligible. Patients will be stratified for exploratory analyses in the analysis phase on the basis of ipsilateral vs bilateral neck irradiation. There will be one treatment group with each patient serving as their own control.

This study will evaluate the response in 10 – 16 patients enrolled at both facilities: St. Joseph's Hospital and Medical Center in Phoenix and Banner – University Medical Center in Tucson (details and justification of sample size in statistical methods) to determine if the proposed everolimus dosing schedule of 5 days is sufficient to show recovery of salivary gland function to pre-treatment levels.

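### The 3 + 3 has no DLT limit at 10 mg and expands 5 mg to ten patients after 2 DLTs, and Section 9.1 lacks the de-escalation and closure rules that Section 11.4 says it contains

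*Protocol*

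**What the plan says.** The initial objective in Protocol Section 3 is to "Document the safe everolimus dose (5 mg versus 10 mg) to be used in the post radiation or chemoradiation setting". The same sentence names a 3 + 3 as the method. The primary recovery objective follows once that dose has been defined.

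Sections 4.1, 6.1 and 9.1 give the same DLT rules, all applied to the 5 mg cohort:

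- 0 DLTs in three patients: escalate to 10 mg.
- 1 DLT in three: add three patients. With no further DLT, escalate; with another, stay at 5 mg and expand to ten.
- 2 DLTs: "If 2 DLT occur, no escalation to full dose (10 mg po daily) will be attempted, and cohort will be expanded to 10 patients".

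For the 10 mg cohort, Section 9.1 gives only a number to enrol. On the longest path: "Subsequently, 10 additional patients will be enrolled in the 10 mg cohort, for a maximum total of 16 patients". The total "can range from a minimum of 10 to a maximum of 16 total patients".

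Section 11.4, on study closure, reads in full: "Please see section 9.1 for escalation and de-escalation procedure which may include study closure as determined by occurrence of dose limiting toxicities". Section 11.5 lists, among the contents of the monthly DSMB reports, "protocol pre-determined early stopping rules for safety or treatment-emergent adverse events", and the status of the study against stopping rules.

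One cohort-level dose reduction exists, at the end of Section 4.1: "if mucositis worsens in 2 out of the first 6 patients, then everolimus 50% dose reduction will be implemented".

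**The concern.** A 3 + 3 design uses DLT counts at each dose to decide whether that dose is tolerable. Here the counts at 5 mg decide only whether 10 mg opens, and no count at 10 mg decides anything. Section 9.1 refers to ten patients at the selected dose, so 10 mg is in effect selected before any patient in this trial has taken it. At 5 mg the rule runs the wrong way for safety: the result that marks the dose as too toxic for escalation is also the result that puts more patients on it.

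Section 11.4 presents Section 9.1 as holding the de-escalation and closure procedure. A board that follows the reference finds neither. This is not detail left to a statistical analysis plan, because the protocol names its own Section 9.1 as the source. At stake are the exposure of patients who have just finished curative-intent radiotherapy, and whether 10 mg could be called a safe dose on the basis Section 3 claims.

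**Working it through.** **The plan's own figures.** The branch totals reproduce: 3 + 10 = 13, 10, 6 + 10 = 16, and 10. The precision statement also reproduces: 1/√10 = 0.316, stated as 0.32. No branch ends below ten patients, so the stated range of 10 to 16 leaves no room for closure. Three DLTs in the first three patients have no branch of their own.

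**What a limit at 10 mg would do.** Apply to 10 mg the count rule already used at 5 mg: continue on 0/3, or on 1/3 followed by 0 in the next three; otherwise stop. For a true DLT rate p (assumed, since the protocol gives none):

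- Stop after three: 3p²(1−p) + p³
- Stop after six: 3p(1−p)² × [1 − (1−p)³]
- Total stop probability: 1 − [(1−p)³ + 3p(1−p)⁵]

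Example at p = 0.20: 1 − [0.512 + 0.6 × 0.328] = 1 − 0.709 = 0.291.

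A stop after three spares 7 of the ten patients and a stop after six spares 4. The mean spared, given a stop, is (7 × stop₃ + 4 × stop₆) / total.

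| Assumed p at 10 mg | Stop after 3 | Stop after 6 | Total | Mean spared, given a stop |
|---|---|---|---|---|
| 0.05 | 0.007 | 0.019 | 0.027 | 4.8 |
| 0.10 | 0.028 | 0.066 | 0.094 | 4.9 |
| 0.20 | 0.104 | 0.187 | 0.291 | 5.1 |
| 0.30 | 0.216 | 0.290 | 0.506 | 5.3 |
| 0.40 | 0.352 | 0.339 | 0.691 | 5.5 |
| 0.50 | 0.500 | 0.328 | 0.828 | 5.8 |

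These probabilities are conditional on 10 mg having opened. As written, no DLT count stops the cohort. The chance of 2 or more DLTs among ten patients is 0.62 at p = 0.20 and 0.99 at p = 0.50, with 2 and 5 DLTs expected, and no action is attached to any of these outcomes.

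**The 5 mg expansion.** The formula is the same, with p now the 5 mg rate. The trial expands 5 mg to ten with probability 0.09, 0.29 and 0.83 at assumed rates of 0.10, 0.20 and 0.50. After 2 DLTs in three patients, 10 − 3 = 7 more are treated at that dose. After 1 in three and another in the next three, 10 − 6 = 4 more are.

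**What the mucositis rule covers.** If the first six patients are counted across the trial, the 13-patient path includes 3 at 5 mg and 3 of the ten at 10 mg. The 16-patient path includes 6 at 5 mg and none at 10 mg.

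**The case against.** The strongest reply concerns size and context.

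- **The probabilities are conditional.** The trial reaches 10 mg only after an acceptable result at 5 mg. If both doses share the same DLT rate, the chance of reaching 10 mg and then triggering the rule is s(1 − s), where s is the total stop probability: about 3%, 9%, 21%, 25%, 21% and 14% across the six rates. The largest figures in the table need a toxic 10 mg and a clean 5 mg. This is right.
- **High rates are not supported.** Exposure lasts five days, 10 mg is an approved dose, and Section 8.1.1 puts the commonest related grade 3/4 reactions between 1% and 10% each. Those are per-reaction figures and do not add up to a DLT rate, but they are a fair caution against leaning on 30% to 50%.
- **Other safeguards exist.** Tables 6-1 and 6-2 stop the drug in most individual patients with grade 3 or 4 toxicity. Weekly calls cover cohort management, serious adverse events are reported within 24 hours, the DSMB reviews monthly, and Section 8.2.2 cites a DSMB charter that is not at hand. The mucositis rule covers the leading expected toxicity, and halving 10 mg does return patients to 5 mg. These are real, but they are individual, discretionary or limited to one toxicity. None is the DLT procedure that Section 11.4 places in Section 9.1.
- **Section 11.5 may be a template.** It also lists efficacy and futility stopping rules, so it is weaker evidence than Section 11.4. The contradiction between 11.4 and 9.1 does not depend on it.
- **The 5 mg expansion is openly stated.** It is a deliberate choice at half the approved dose. Even so, expanding a dose after 2 DLTs in three patients is not a 3 + 3.

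**Conclusion.** The point stands and must be fixed. Section 3 claims a design property the rules do not have, and Section 11.4 cites rules that Section 9.1 does not contain; neither conclusion rests on an assumed rate. The practical size does. At true DLT rates of 5% to 10% at 10 mg, a limit would act 3% to 9% of the time once the dose is open. At 20% it would act 29% of the time and at 30% 51%, sparing about five patients on average. The primary recovery estimate is not biased by this, and safety at each dose can still be described. What cannot be supported is a conclusion that 10 mg was shown safe by a 3 + 3 design.

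**What to change.** Choose one of two routes.

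**(a) Supply the rules.** Write into Section 9.1, and repeat in 4.1 and 6.1:

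- a DLT limit at 10 mg, for example the 5 mg rule, with 2 or more DLTs in the first three or six patients returning enrolment to 5 mg;
- a pause or closure with DSMB review after 2 or more DLTs at 5 mg;
- the DLT observation period that must be complete before each step;
- a cross-reference to the mucositis rule, stating whether its six patients are counted per dose;
- a patient range that allows early closure.

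The cost is short enrolment holds after three and six patients at 10 mg, and possibly fewer than ten patients at the chosen dose. With six, the standard error of mean recovery is 1/√6 = 0.41 SD, against 0.32 SD with ten.

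**(b) Correct the claims.** If no such rules are intended, remove the 3 + 3 and safe-dose wording from Section 3, restate the objective as describing DLT frequency at each dose (x/n with an exact 95% confidence interval), and correct Sections 11.4 and 11.5. This changes wording only and leaves exposure at 10 mg without a limit.

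Either route needs an IRB-approved amendment under Section 10. Route (a) is preferable for patient safety. The clinical limit itself is for the investigator and the DSMB to set.
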